1.33.5 Baseline Descriptive Statistics

Demographics and baseline characteristics will be summarized and presented. Age, height, weight, BMI, BMI-SDS, and fat mass percentage at study baseline will be summarized using descriptive statistics (N, mean, SD). The number and percentage of subjects in each sex, ethnicity, and race category also will be presented. Baseline HOMA-IR, fasting glucose and fasting insulin, as well as other measures of metabolism (e.g. cholesterol and triglycerides) will be summarized using descriptive statistics (N, mean, SD).

1.33.6 Planned Interim Analyses

No formal interim analyses are planned for safety, futility or efficacy.

1.33.7 Sub-Group Analyses

The sample size is too small to support meaningful sub-group analyses for age, sex, or race/ethnicity, and no such analyses will be conducted.

1.33.8 Tabulation of individual Participant Data

Individual participant data will not be listed by measure and time point.

1.33.9 Exploratory Analyses

Any of the exploratory evaluations that generate quantitative measures will be examined using descriptive statistics including confidence intervals when appropriate. Any statistical tests (paired t-tests of baseline versus 16-week results) performed for evaluation of exploratory objectives will be done without formal adjustment for multiple comparisons, but in the context of the number of tests performed.

The following dependent variables will be examined in the dataset:

Change in: BMI standard deviation score for age and sex, body weight, percentage total body fat mass by DXA, appetite score using visual analog scale, attention bias to highly palatable images, energy intake at buffet meal, free living physical activity by accelerometry, hemoglobin A1C, plasma GI hormones (GLP-1 and PYY), weight related quality of life score, Beck depression inventory total score, Columbia-Suicide Severity Rating Scale, body-esteem scale score for adolescents and adults, HOMA-IR, fasting glucose and insulin, triglycerides, LDL- and HDL-cholesterol, OGTT glucose and insulin AUC, SomaScan platform.

REGULATORY AND OPERATIONAL CONSIDERATIONS

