Primary Endpoint: Estimation of required sample size for a later RCT through calculation of effect size for change in body mass index (BMI) from baseline to 16 weeks of liraglutide.

Key Secondary Endpoints:

Changes in BMI and fat mass after 16 weeks of liraglutide

Comparison of changes in BMI and fat mass after 16 weeks of liraglutide in participants who had a poor initial response to SG (<20% BMI reduction at BMI nadir) vs. those with a typical post-SG weight loss ($\geq 20\%$ BMI reduction at BMI nadir)

Tolerability and safety of liraglutide 3.0 mg.

Additional (exploratory) Endpoints: Change from baseline to 16 weeks of liraglutide in:

1. Proportion reducing BMI by at least 5% and 10%
2. BMI standard deviation score for age and sex (BMIZ)
3. Body weight
4. Percentage total body fat mass by DXA
5. Appetite score using visual analog scale (VAS)
6. Attention bias to highly palatable images
7. Energy intake at buffet meal
8. Free living physical activity by accelerometry
9. Metabolic syndrome markers (waist circumference, systolic and diastolic blood pressure, lipids, fasting plasma glucose level)
10. Fasting plasma insulin and HOMA-IR index
11. 2-hour oral glucose tolerance test (OGTT) insulin and glucose measurements
12. Hemoglobin A1C
13. Plasma GI hormones (GLP-1 and PYY) during OGTT
14. Weight related quality of life (QoL) score
15. Beck Depression Inventory total score
16. Body-Esteem Scale Score for Adolescents and Adults
17. Columbia Suicide Severity Rating Scale
18. Secretome analysis
19. Stool microbiome analysis

Study Population:

Up to a total of 50 male and female adolescents age < 21 years old from Washington D.C., Maryland, and Virginia who underwent SG at least 1 year prior to enrollment and have BMI ≥ 30 kg or $\geq 95^{\text{th}}$

Abbreviated Title: Liraglutide in Teens Post-SG

Version Date: 1/30/23

percentile for age and sex in order to enroll at least 40 who are eligible and agree to take liraglutide for 16 weeks.

Phase:

Phase II

Description of Sites/Facilities

We will primarily recruit participants who previously underwent SG from Children's National Hospital (CNH), in Washington, DC, a high-volume pediatric bariatric surgery center in our area.

Enrolling Participants:

Participants will be assessed at the NIH Clinical Center for all study visits. Eligible participants may also be interviewed by telephone.

Description of Study Intervention:

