The SF-10 Health Survey for Children is a parent-completed survey that contains 10 questions adapted from the Child Health Questionnaire. The SF-10 provide coverage across a wide range of domains and is scored to produce physical and psychosocial health summary measures. The SF-10 will be conducted in participants <18 years of age according to the SOA.

Mental Health Assessments-

Beck Depression Inventory (BDI-II)-

The Beck Depression Inventory (BDI) is a 21-item, self-report rating inventory that measures characteristic attitudes and symptoms of depression [83]. BDI-II was revised in 1996 to be more consistent with DSMIV criteria for depression in adolescents and adults (age 13-80) [84].

Columbia-Suicide Severity Rating Scale (C-SSRS)

The C-SSRS is a tool used not only to predict suicide attempts but to assess the full range of evidence-based ideation and behavior items, with criteria for next steps (e.g., referral to a mental health professional [MPH]). There are 2 versions of the C-SSRS that will be administered according to the SOA:

- 1) **The Baseline/Screening** version of the scale combines the Baseline and Screening forms to assess suicidality in a patient's lifetime and during a predefined time. This version can assess a patient's lifetime suicidality for data collection purposes as well as eligibility based on inclusion/exclusion criteria.
- 2) The **Since Last Visit** version of the scale assesses suicidality since the patient's last visit. This version is meant to assess participants who have completed at least one initial C-SSRS assessment and will be used in every subsequent visit. The 'Since Last Visit' version of the C-SSRS is asking about any suicidal thoughts or behaviors the patient/participant may have had since the last time the C-SSRS was administered.

To be eligible for the study, a patient cannot have a suicidal ideation of type 4 or 5, any lifetime history of a suicide attempt, or any suicidal behavior in the last month.

Hollingshead Two Factor Index of Socioeconomic Status [85] will be obtained for the parents/guardians of the participant.

Body-Esteem Scale for Adolescents and Adults

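### The C-SSRS is planned as a change from baseline to 16 weeks, but its two forms cover different recall periods, so a mean change can be biased in either direction

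*Combined protocol and SAP*

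**What the plan says.** The synopsis (section 1.1) lists "17. Columbia Suicide Severity Rating Scale" among the exploratory endpoints headed "Change from baseline to 16 weeks of liraglutide in". Section 1.33.9 repeats it in its list of change variables, "Beck depression inventory total score, Columbia-Suicide Severity Rating Scale". That section says quantitative exploratory measures "will be examined using descriptive statistics including confidence intervals when appropriate". On testing it refers to "Any statistical tests (paired t-tests of baseline versus 16-week results) performed for evaluation of exploratory objectives", and it names no other test. Section 1.33.1 sets testing at one-sided 5%; no direction is given for the C-SSRS.

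Section 1.26.1 describes two forms. The Baseline/Screening form is meant to "assess suicidality in a patient's lifetime and during a predefined time"; the length of that second period is not given. The Since Last Visit "version of the scale assesses suicidality since the patient's last visit", and the text has it used at each later visit. The schedule in section 1.3, whose columns are broken in the extracted text, shows only two marks for the scale. Section 1.33.4 (safety analyses) covers adverse events, laboratory values and vital signs, and does not name the C-SSRS.

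**The concern.** A change score has meaning only if both values measure the same thing over comparable time. Here the first value can cover a lifetime or a recent period of unknown length, and the second covers whatever time has passed since the last administration. The difference can move away from zero when nothing about the participant has changed. Section 1.26.1 describes ideation types and behaviour items but no total, so the quantity to be averaged is also undefined. The Beck inventory, listed just before it in section 1.33.9, is specified as a total score.

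This is the trial's suicidality instrument, in adolescents. Section 1.27 treats it as a safety assessment with same-day scoring. A reader of the results would want to know how many participants had ideation or behaviour on treatment and how severe it was. A mean change does not answer that and can hide a single new severe case.

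**Working it through.** The plan states no figure on this point, so the check sets the sections side by side and then illustrates the size under assumptions.

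**Follow-up window.** Visit 5 is Day 112 ± 10 (section 1.3).
- Two administrations, baseline form at Visit 1: 112 − 10 = 102 to 112 + 10 = 122 days.
- Two administrations, baseline form at screening (up to 28 days earlier, section 1.25.2, taking enrolment as Visit 1): up to 122 + 28 = 150 days.
- Administration at every visit (section 1.26.1): nominally 112 − 84 = 28 days, from Visit 4 to Visit 5.

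**Baseline window.** Either lifetime or the predefined period. The documents do not say which enters the change, or how long the second one is.

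**Illustration.** Assume a constant ideation rate with no true change, a yes/no score for any ideation in the window, independent occasions, and monthly (30-day) probabilities *p* of 2%, 5% and 10%. None of these is in the documents. The probability of ideation in *d* days is P(d) = 1 − (1 − p)^(d/30). For example, at p = 5%, P(112) = 1 − 0.95^(112/30) = 0.174, so a 30-day baseline gives an expected change of 0.174 − 0.050 = +0.124.

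| Baseline window → follow-up window | p = 2% | p = 5% | p = 10% |
|---|---|---|---|
| 30 days → 112 days | 0.073 − 0.020 = +0.053 | 0.174 − 0.050 = +0.124 | 0.325 − 0.100 = +0.225 |
| Lifetime, taken as 1 year at risk → 112 days | 0.073 − 0.218 = −0.145 | 0.174 − 0.464 = −0.290 | 0.325 − 0.722 = −0.397 |
| 30 days → 28 days | 0.019 − 0.020 = −0.001 | 0.047 − 0.050 = −0.003 | 0.094 − 0.100 = −0.006 |

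In 20,000 simulated trials of 40 participants per scenario, a paired t-test at one-sided 5% called the false rise in the first row significant in 29%, 56% and 81% of trials. It called the false fall in the second row significant in 60%, 88% and 98%. In the third row, significance in either given direction occurred in 1.6% to 5.9% of trials.

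**What a mean can hide.** Suppose, as an assumption, that ideation is scored by its type number with 0 for none. One participant moving from 0 to 5 adds +5. Five participants moving from 1 to 0 add −5. The mean change over 40 is (5 − 5)/40 = 0. The entry criteria (sections 1.11 and 1.26.1) exclude ideation of type 4 or 5 and any past attempt, so any such event after entry is new, and it is the kind of event that averaging dilutes.

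**The case against.** The strongest reply is that the plan commits to very little here. Testing is conditional, section 1.33.1 summarises categorical variables as number and percentage per category, and a careful analyst might simply tabulate the C-SSRS. That is fair about the t-test. But the listed variable is still the change, and a descriptive mean change has the same window problem.

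Second, the windows may roughly match. If the scale is given at every visit and the predefined period is about a month (the behaviour exclusion uses the last month), the third row of the table applies and the bias almost vanishes. That possibility stands, but the plan does not secure it. In that case the 16-week form would also cover only the last 28 of 112 days, and a baseline-to-16-week change would leave out the first 112 − 28 = 84 days on drug.

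Third, a reader might infer that new suicidality would otherwise go uncounted. The documents do not support that. Section 1.27 has concerning scores escalated the same day, and sections 1.22 and 1.28.6 make new clinically relevant findings adverse events. Section 1.33.4 then tabulates treatment-emergent events by System Organ Class. What is missing is a summary specific to the C-SSRS.

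Fourth, a reader might infer that the trial is set to report a significant fall in suicidality. No section says lifetime items enter the change; section 1.26.1 links them to data collection and eligibility. A false fall is one possible result of an unspecified analysis, not a planned one. Nor does the depression row of the label table in section 1.17.2.2 (4.0% versus 2.4%, about 5 of 125 versus 3 of 126) say anything about suicidality.

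Finally, the item is exploratory in a single-arm pilot, and no success or stopping rule uses the scale's change score. That limits the consequence.

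**Conclusion.** The concern holds in a bounded form. As written, the baseline-to-16-week change in C-SSRS is not interpretable: the two forms have different recall periods, the baseline period is not chosen or given a length, and no score is defined. The bias can go either way. Its size cannot be fixed from the documents, partly because sections 1.26.1 and 1.3 disagree on the number of administrations and must be reconciled. The illustrative range, from a false rise of 22.5 points to a false fall of 39.7 points with near zero for matched windows, rests on assumed rates, a yes/no score and independent occasions. That unequal windows distort the change does not depend on those rates. The defect lies in the reported C-SSRS result, not in individual follow-up or adverse event capture. It should be corrected, though it does not affect the primary endpoint.

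**What to change.** - **Section 1.33.9, with the matching entry in the synopsis:** remove the C-SSRS from the change variables and from the paired t-tests.
- **Section 1.33.4:** report, in the Safety dataset, the number and percentage of participants with any on-treatment suicidal ideation by worst category, and with any suicidal behaviour, with exact confidence intervals. For scale, 0 of 40 would carry a two-sided 95% upper limit of 1 − 0.025^(1/40) = 8.8%.
- **Shift tables:** show worst on-treatment category against both the lifetime and the recent-period baseline, as description only. State the length of each recall window and make no significance test of change. Using the recent-period baseline alone would set a short window against about 16 weeks and lean towards a false rise, so both references are needed.
- **Sections 1.26.1 and 1.3:** reconcile the frequency of administration, and state the length of the predefined period and the visit at which the baseline form is completed. If that is screening, note that the first follow-up window includes days before the first dose.

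Taking the worst category over all forms up to Visit 5 spans the whole interval from the baseline form under either schedule, if no form is missed, so the count depends less on the unresolved frequency than a change score does.

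The analysis change is wording only and needs no new data. The cost is that no single mean-change figure is given for this exploratory item.

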1.34 INFORMED CONSENT PROCESS

1.34.1 Consent/Accent Procedures and Documentation

In obtaining and documenting informed consent, all study staff will comply with applicable regulatory requirements (e.g., 45 CFR Part 46, 21 CFR Part 50, 21 CFR Part 56) and will adhere to ICH GCP.

Informed consent is a process that is initiated prior to the individual's agreeing to participate in the study and continues throughout the individual's study participation. Consent and Assent forms will be Institutional Review Board (IRB)-approved and the participant (and/or parent/guardian) will be asked to read and review the documents. The principal investigator or associate investigators with appropriate expertise will obtain written, active consent before the Screening Visit or as the first activity conducted at the Screening Visit. The purpose of the project, all testing procedures, and study components, and of their rights as research participants, will be described in detail in terms suited to the participant's comprehension. Potential participants and their parents will also be informed of the possible risks and inconveniences of the study. The investigator will answer any questions that may arise. The investigator will also explain the study assent form to minors using appropriate language. Sufficient time and opportunity will be given for discussion of the research as well as to answer any questions all may have, taking care to minimize or eliminate the perception of coercion or undue influence.

Participants will have the opportunity to carefully review the written consent form and ask questions before signing. The participants will have the opportunity to discuss the study with their family or surrogates and given time to think about it prior to agreeing to participate. The participant (or parent/guardian) will sign the informed consent document prior to any procedures being done specifically for the study. Participants will be informed that participation is voluntary and that they may withdraw from the study at any time, without prejudice. The rights and welfare of the participants will be protected by emphasizing to them that the quality of their medical care will not be adversely affected if they decline to participate in this study. The informed consent form (and assent if applicable) will be signed before the participant undergoes any study-specific procedures. The investigator-designated research professional obtaining the consent (and assent if applicable) must also sign the informed consent and assent form (if applicable). A copy of the informed consent/assent documents will be given to the participants for their records. The informed consent process will be documented in the medical record (including the date), and the original completed forms will be kept in the participant's medical record with a copy in their research chart.

Informed consent documents (and assent documents, if applicable) may be printed to sign and date in ink, or the electronic documents may be signed with a hand signature using a finger, mouse or stylus via an approved platform. Participants may be asked to complete the consent process electronically via iMed and DocuSign, which are both 21 CFR Part 11 compliant. Once identity is confirmed, consents can be electronically signed, date-stamped, and routed to the PI for electronic signature. Once the PI has logged into the secure site and digitally signed the consent, a pdf of the signed consent is created. As is done for forms signed in ink, the participant will be provided with a copy of the signed document, and can also contact our study staff to obtain a hard copy of the consent at any point in this process.

Abbreviated Title: Liraglutide in Teens Post-SG

Version Date: 1/30/23

For assent of children

All adolescent participants are expected to be able to comprehend and be included in all discussions about the trial. Age-appropriate language will be used to describe the procedures and tests involved in this study, along with the risks, discomforts, and benefits of participation. All child study participants, who will be between age 12 and <18 years will be asked to sign an age appropriate assent form. The consent/assent process will be documented in the child's medical record. All children will be contacted after they have reached the age of 18y to determine whether they wish to continue participating in the trial; informed consent will be obtained from them at that time.

Telephone consent

In certain instances, the PI or designee will obtain informed consent by a telephone or video conversation with a protocol-eligible subject who cannot travel to the NIH Clinical Center for a considerable period of time. A parent/guardian will be involved if the subject is <18 years of age.

The informed consent document will be sent to the subject by mail, email, or fax. An explanation of the study will be provided over the telephone or other electronic media (via an NIH approved remote platform) after the subject has had the opportunity to read the consent form. The informed consent form will be signed and dated.

The original informed consent document will be sent back to the consenting investigator who will sign and date the consent form with the date the consent was returned.

A fully executed copy will be returned via mail for the subject's records.

The informed consent process will be documented on a progress note by the consenting investigator.

The investigator will confirm that, when required, written legally effective consent has been obtained prior to initiating any study interventions.

Telephone assent

The informed consent and assent documents will be sent to the parents/guardian and child. An explanation of the study will be provided over the telephone after the parents/guardian and child have had the opportunity to read the documents. Age-appropriate language will be used to discuss the study with the child. The parents/guardian will sign and date the informed consent. The child will sign and date that form. All children will be contacted after they have reached the age of 18y to determine whether they wish to continue in the trial and informed consent will be obtained from them at that time.

The original signed informed consent and assent documents will be sent back to the consenting investigator who will sign and date the consent form with the date the consent was returned.

A fully executed copy will be returned via mail to the subject.

The informed consent and assent process will be documented on a progress note by the consenting investigator.

Abbreviated Title: Liraglutide in Teens Post-SG

Version Date: 1/30/23

1.34.2 Consent for minors when they reach the age of majority

When a pediatric subject reaches age 18, continued participation (including ongoing interactions with the subject or continued analysis of identifiable data) will require that consent be obtained from the now adult with the standard protocol consent document to ensure legally effective informed consent has been obtained.

If reconsent is not feasible, we request waiver of informed consent to continue to use data and/or specimens for those individuals who become lost to follow up or who have been taken off study prior to reaching the age of majority.

Requirements for Waiver of Consent consistent with 45 CFR 46.116 (d):

- (1) The research involves no more than minimal risk to the subjects.
 - a. Analysis of samples and data from this study involves no additional risks to subjects.
- (2) The research could not practicably be carried out without the waiver or alteration.
 - a. Considering the length of time between the minor's last contact with the research team and their age of majority, it will likely be very difficult to locate them again. A significant reduction in the number of samples analyzed is likely to impact the quality of the research.
- (3) As the research involves using identifiable private information or identifiable biospecimens, the research could not practicably be carried out without using such information or biospecimens in an identifiable format.
 - a. Though the purpose of future studies cannot yet be known, they often involve the correlation of clinical outcomes and clinical interventions with laboratory studies. Such information would be unavailable if access to medical record numbers was unavailable.
- (4) The waiver or alteration will not adversely affect the rights and welfare of the subjects.
 - a. Retention of these samples or data does not affect the welfare of subjects.
- (5) Whenever appropriate, the subjects will be provided with additional pertinent information after participation.
 - a. We only request a waiver of consent for those subjects who have been lost to follow-up or who have been taken off study prior to reaching the age of majority.

